1. SYNOPSIS

Study Objective	To evaluate benefits of a Healing Ointment in skin improvement after dermatologic procedures
Methodology	Multi-center, prospective study
Number of Subjects at the end	20 subjects to complete
Study duration	28 days
Test product	Cetaphil® Healing Ointment
Conditions of use	Twice daily topical application and as needed
Study visits	Day 0, day 7 or 14, day 28
Specific Inclusion Criteria:	
 ○ Demographics and study skin conditions 
 - Any race and ethnicity (to be recorded) - Fitzpatrick skin type (to be recorded) - Women or men - Age: 18 to 85 years old - Subject who undergo Mohs surgery, skin biopsy, excision on the head/neck or body ○ Administrative 
 - Ability of giving consent for participation in the study - Agreement to adhere to the procedures and requirements of the study and to report to the institute on the day(s) and at the time(s) scheduled for the assessments.
Specific Exclusion Criteria:	
 - History of allergy or hypersensitivity to cosmetic ingredients - Pregnant, planning pregnancy during the course of the study or breastfeeding - Subject with a history of keloids or hypertrophic scars - Presence of tattoo and/or scar in the treatment area that in the investigator's opinion would interfere with study assessments - Subjects with history of or the presence of any skin condition/disease that might interfere with the diagnosis or

Protocol Version 1:

This document contains confidential, proprietary information.

	
evaluation of study parameters (i.e., atopic dermatitis, eczema, psoriasis, seborrheic dermatitis) at the discretion of the investigator.
 
 - Subjects with inability to comply with all study protocol restrictions and visits

Procedure
	
 - Subjects will report to the site as screening visit, will be given an informed consent form, HIPAA form, photography release form, Code of Conduct form, and medical history form to complete. - Subjects will be screened on the basis of the selection criteria for study qualification. At day 0, investigator assessment (erythema, edema, scabbing/crusting, and overall wound appearance) and subjective tolerability assessment (burning, itching, pain) will be performed based on 0-4 analog scale. - Subjects will undergo the assigned surgical procedure. - After procedure, photography of the surgical site, investigator assessment and subjective tolerability will be performed, and investigator or staff will apply Healing Ointment immediately followed by a standard bandage. - Subjects will be instructed to apply the provided Healing Ointment to the wound at least twice daily and reapply as needed. - Subjects to return to the site at day 7 (\pm 2 days for head/neck group) or day 14 (\pm 2 days for body group), and day 28 post-treatment (\pm 3 days) for follow-ups. - For each follow-up visit, investigator will perform objective assessment and photography. Subjects will perform additional subjective tolerability assessment and self-assessment questionnaire.

Statistical analysis
	
Clinical grading and questionnaire.

APPENDIX II: SELF-ASSESSMENT QUESTIONNAIRE28

3. LIST OF ABBREVIATIONS AND DEFINITIONS OF TERMS

AE	Adverse Event
°C	Degrees Celsius
CRF	Case Report Form
etc.	et cetera
e.g.	for example (Latin; exempla gratia)
°F	Degrees Fahrenheit
GCP	Good Clinical Practice
HA	Hyaluronic Acid
HIPAA	Health Insurance Portability and Accountability Act of 1996
ICF	Informed Consent Form
ICH	International Conference on Harmonization
ICT	Information and communication technologies
i.e.	that is (Latin; id est)
IEC	Independent Ethics Committee
IRB	Institutional Review Board
N or n	Number
%	percent
SAE	Serious Adverse Event
SD	Standard deviation
SOP	Standard Operating Procedure

Protocol GLI.04.US.SL.017

CONFIDENTIAL

4. BACKGROUND AND RATIONALE

Post-surgical wound care is imperative to promote rapid healing without complications. The key principle of wound management is to create an occlusive, clean, and moist environment at the wound site to reduce the possibility of infection and facilitate the wound healing phases.¹ Two (2) common topical applications to achieve this optimal condition are topical antibiotics and over-the-counter (OTC) petrolatum-based ointments. While both methods have comparable wound-healing properties, topical antibiotics have been shown to potentially cause drug resistance or allergic contact dermatitis.²⁻⁴ For this, dermatologists often opt for petrolatum-based ointment application for wound healing.

Cetaphil® Healing Ointment (Galderma, Fort Worth, TX) is an OTC skin protectant that contains 71.5% petrolatum, shea butter to soften, smooth and hydrate, as well as vitamin E to help support moisture barrier function. The Healing Ointment has been clinically proven to hydrate the skin's natural barrier for 48 hours while quickly protecting and healing dry, irritated skin for visible improvement in 1 week. The product is also hypoallergenic, non-comedogenic, gentle on sensitive skin and accepted by the National Eczema Association. These beneficial properties make Cetaphil® Healing Ointment an ideal candidate as a post-surgical wound care. This study is to investigate safety and efficacy of Cetaphil® Healing Ointment in wound healing after dermatologic procedures.

5. STUDY OBJECTIVE AND CLINICAL HYPOTHESIS

5.1 Study Objective

To evaluate safety and efficacy of a Healing Ointment in skin improvement after dermatologic procedures such as Mohs surgery, skin biopsy, excision on the head/neck or body.

5.2 Clinical Hypothesis

The Healing Ointment, consisting of skin protectant petrolatum and other beneficial ingredients, will be able to protect and promote healing of the wound site post-surgery.

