6. SELECTION AND DISPOSITION OF STUDY POPULATION

6.1 Number of Subjects

A maximum 20 subjects to complete the study, in which 10 subjects with dermatologic procedure on the head/neck and 10 subjects with dermatologic procedure on the body.

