7.2 Additional Products and Materials

The Sponsor will only provide Cetaphil® Healing Ointment for the study. The study overhead will cover any additional materials or supplies.

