7.4 Method of Treatment Assignment

Subjects will be numbered sequentially in the order in which they qualify for entry into the study.

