11. STATISTICAL ANALYSIS

A descriptive statistical summary will be provided for clinical grading and tolerability assessments. The descriptive summary will be performed for each parameter, including N, mean, median, standard deviations, minimum, and maximum of values at all applicable time points.

Mean of the change from baseline (pre-procedure) will be estimated at applicable post-baseline time point. The null hypothesis, that the mean change from baseline (pre-procedure) is zero, will be tested using methods described in the Statistical Analysis Plan table.

The following will be calculated and reported for each evaluation parameter at applicable post-baseline (pre-procedure) time point:

$$\text{Percent mean change from baseline} = \frac{(\text{postprocedure or visit mean score} - \text{baseline preprocedure mean score})}{\text{baseline preprocedure mean score}} \times 100$$

$$\text{Percent of subjects improved/worsened} = \frac{(\text{number of subjects improved/worsened from baseline preprocedure})}{\text{total number of subjects}} \times 100$$

Questionnaires will be tabulated, and the percentage of all response options (favorable and unfavorable) will be reported for each question and each timepoint.

Statistical Analysis Plan

Evaluation	Change from Baseline Pre-Procedure	Notes/Interpretation
Clinical grading	Paired t-test; If normality fails, a Wilcoxon signed-rank test will be used.	A decrease in scores indicates an improvement
Tolerability assessment	Paired t-test; If normality fails, a Wilcoxon signed-rank test will be used.	A decrease in scores or lack of significant increase indicates tolerability/safety of the treatment product
Self-assessment questionnaire	N/A	Percentage of favorable and unfavorable responses will be provided for each question.

All statistical tests will be 2-sided at significance level alpha = 0.05 unless specified otherwise. *P* values will be reported to 3 decimal places.

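### The healing hypothesis is tested only by within-subject change in one uncontrolled arm, so no result in either direction can be attributed to the ointment

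*Combined protocol and SAP*

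**What the plan says.** The aim is causal. Section 4 states "This study is to investigate safety and efficacy of" the product in wound healing. Section 5.1 gives the objective as "To evaluate safety and efficacy of a Healing Ointment in skin improvement after dermatologic procedures", and Section 5.2 predicts that the ointment "will be able to protect and promote healing of the wound site post-surgery".

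The design has one arm. The synopsis calls it a "Multi-center, prospective study" and names no comparator. Under the heading on treatment assignment, Section 7.4 says only: "Subjects will be numbered sequentially in the order in which they qualify for entry into the study". Section 7.2 adds: "The Sponsor will only provide Cetaphil® Healing Ointment for the study". Section 6.1 plans at most 20 completers, 10 with head/neck procedures and 10 with body procedures. These groups are anatomical, not treatment groups.

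Section 11 tests a null of zero mean change by paired t-test, or by Wilcoxon signed-rank test if normality fails, two-sided at 0.05. The reference is the score taken before the procedure. For clinical grading the interpretation column reads: "A decrease in scores indicates an improvement". A post-procedure score is also graded (Sections 9.1.2 and 10.1), but the percent-change formula in Section 11 treats it as one of the later scores compared with the pre-procedure one.

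**The concern.** A claim that a product promotes healing is a claim about what would have happened without it. Nothing in this plan supplies that comparison. Each subject also has the lesion treated, a standard bandage applied (Section 9.1.2) and instructions for cleaning the site (Section 8.3.1), and the wound heals over the same 28 days. Within-subject change mixes all of these with any ointment effect.

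The choice of reference adds a second difficulty. The pre-procedure score describes the skin with its lesion, before there is a surgical wound. Change from it mainly shows whether the lesion graded higher or lower than the healing site does later. It does not measure healing of the wound that Section 5.2 is about.

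What is at stake is the conclusion. A significant decrease could be reported as efficacy of an inert ointment, and an effective ointment could show a significant worsening.

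**Working it through.** The plan gives no effect size, SD, power or sample-size derivation, so there is no figure of its own to reproduce. All means and SDs below are assumptions. Only n = 20, the two-sided 0.05 level, the paired test and the choice of reference come from the documents (Sections 6.1 and 11).

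**Step 1: the planned test with no ointment effect.** For mean change m and SD of change s, the paired t statistic has noncentrality (m/s) × √20 on 19 degrees of freedom, and is significant beyond ±2.093. For |m| = 0.5:

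- s = 0.6: 0.5/0.6 × 4.472 = 3.73
- s = 0.8: 0.5/0.8 × 4.472 = 2.80
- s = 1.0: 0.5/1.0 × 4.472 = 2.24

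For |m| = 1.0 each value doubles. The noncentral t distribution then gives:

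| Reference and assumed mean scores | m | P(significant decrease), s = 0.6 / 0.8 / 1.0 | P(significant increase), s = 0.6 / 0.8 / 1.0 |
|---|---|---|---|
| Pre-procedure 0, Day 28 0.5 | +0.5 | about 0 | 0.942 / 0.755 / 0.564 |
| Pre-procedure 0, Day 28 1.0 | +1.0 | about 0 | 1.000 / 1.000 / 0.989 |
| Pre-procedure 0.5, Day 28 0.5 | 0 | 0.025 throughout | 0.025 throughout |
| Pre-procedure 1.0, Day 28 0.5 | −0.5 | 0.942 / 0.755 / 0.564 | about 0 |
| Post-procedure 2.0, Day 28 1.0 (not a planned test) | −1.0 | 1.000 / 1.000 / 0.989 | about 0 |

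The likely direction depends only on whether the pre-procedure mean lies below or above the Day 28 mean. The SD changes the probability, not the direction. Where every site scores 0 before surgery, a decrease is impossible because 0 is the floor of the scale.

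**Step 2: check on a bounded scale.** Scores were simulated on a 0 to 3 half-point scale (n = 20, 2,000 runs per scenario, SD 0.5 per visit, or 0 where the pre-procedure score is 0). Against the pre-procedure score:

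- 1.0 to 0.5 gave a significant decrease in 0.82 of runs
- 0.5 to 0.5 gave a significant decrease in 0.03
- 0 to 0.5 gave a significant increase in 1.00

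The last figure exceeds the table's range because a pre-procedure score with no spread makes the SD of change smaller.

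**Step 3: could the same 20 subjects supply a control?** By the normal approximation, n per arm = 2 × (1.960 + 0.842)² / d². For an assumed standardised difference d = 0.5 this is 15.70/0.25 = 62.8, so 63 per arm. For d of 0.3, 0.8 and 1.0 it is 175, 25 and 16. With 10 per arm, power at d = 0.5 is Φ(0.5 × √5 − 1.960) = Φ(−0.842) = 0.20.

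**The case against.** The strongest defence is that the plan claims less than this point implies. "A decrease in scores indicates an improvement" can be read as a note on scale direction; unlike the tolerability row, it does not mention the product. Section 5.2 is headed as a clinical hypothesis, and the statistical null is stated separately in Section 11. No sentence says that rejecting the null demonstrates efficacy, and a 20-subject uncontrolled study is an ordinary way to describe experience with a marketed product.

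Part of this stands: the plan does not state the faulty inference outright. But the objective and hypothesis are causal, and no other analysis bears on them with a comparison. The questionnaire is only tabulated. Its one comparative item (Appendix II) asks for preference over a previous product, not for healing outcomes. A reader of the report would have only the within-subject test to set against Section 5.2.

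A stronger reading is tempting: that normal healing alone would make the planned test positive, so that a very small p-value should be expected even from an inert ointment. The documents do not support it. It needs a fresh-wound reference, and Section 11 uses the pre-procedure score. Healing brings scores back toward that reference: full return gives a significant decrease at the nominal 0.025, and residual signs over a low pre-procedure score push the result toward an increase. A decrease becomes likely without an ointment effect only where the lesion itself graded above the healed level, and that reflects lesion removal as well as healing.

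**Conclusion.** The point holds as a limit on attribution. With one arm and no external standard, no result of the Section 11 test, in either direction, can support or refute Section 5.2 or the efficacy part of Section 5.1. This follows from the design and rests on no assumed score.

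The probabilities in the working only illustrate how the test can mislead. With no ointment effect it may show a significant worsening or a significant improvement, each with probability 0.56 to 0.94 under the mirror-image scenarios, depending on how the lesion graded before surgery. They assume the stated means, an SD of change of 0.6 to 1.0 and 20 analysed subjects.

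The near-certain rejection for a fall from 2.0 to 1.0 belongs to a post-procedure contrast that the plan does not test. It shows that changing the reference alone would not make the result attributable to the ointment.

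**What to change.** - **Sections 5.1 and 5.2:** restate as descriptive, for example: *to describe the course of wound signs and symptoms over 28 days in subjects using the ointment*. Align Section 4 and the synopsis.
- **Section 11, reference:** describe healing as mean change from the post-procedure score to Day 7/14 and Day 28, with 95% confidence intervals. Keep change from the pre-procedure score only as a description of return to the pre-surgical state.
- **Section 11, interpretation column for clinical grading:** replace the present sentence with *a decrease indicates lower severity and does not show a product effect*.
- **Section 11, p-values:** state that p-values against zero change, from either reference, are not evidence that the ointment promotes healing.

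The cost is wording, one additional summary of scores already collected, and a weaker claim. No extra subjects, visits or assessments are needed. If the causal claim must be kept, a concurrent control is required. Splitting the planned 20 subjects would not suffice, with about 20% power at an assumed difference of 0.5 SD, so the descriptive restatement is the realistic route at this size.

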6. SELECTION AND DISPOSITION OF STUDY POPULATION

6.1 Number of Subjects

A maximum 20 subjects to complete the study, in which 10 subjects with dermatologic procedure on the head/neck and 10 subjects with dermatologic procedure on the body.

6.2 Study Population Characteristics

Males and females who undergo Mohs surgery, skin biopsy, or excision on the head/neck or body (inclusive and a good ratio of each surgical type within the study panel).

6.3 Inclusion Criteria

1. Subjects of 18 to 85 years of age.
2. Subjects with a clinical diagnosis that requires invasive procedure such as Mohs surgery, skin biopsy, excision on the head/neck or body.
3. Subjects of any gender.
4. Subjects of any race and ethnicity.

Protocol Version 1:

This document contains confidential, proprietary information.

Protocol GLI.04.US.SL.017

CONFIDENTIAL

5. Subjects of any Fitzpatrick skin type.
6. Subjects who are able and willing to provide written informed consent prior to any study related procedures.
7. Subjects who agree to be photographed at each visit.
8. Subjects apprised of the Health Insurance Portability and Accountability Act of 1996 (HIPAA) and applicable state Bill of Rights.
9. Subjects who agree to adhere to the procedures and requirements of the study, to report to the institute on the day(s) and at the time(s) scheduled for the assessments, and to complete all required visits.

6.4 Exclusion Criteria

1. Subjects with history of allergy or hypersensitivity to cosmetic ingredients or skincare products.
2. Subjects who are pregnant or breast-feeding, or who plan to become pregnant or breast feed during the course of the trial.
3. Subjects with a history of keloid or hypertrophic scars.
4. Subjects with presence of tattoo and/or scar in the treatment area that in the investigator's opinion would interfere with study assessments.
5. Subjects with any diseases, condition or presentation that may, in the opinion of the investigator, may put the subject at risk, may confound study results, or may interfere with participation in the study.
6. Subject with inability to comply with all study protocol restrictions and visits.
7. Subjects that are relatives of the investigator or are themselves or a relative of any study staff or any Galderma employee.
8. Subjects who have participated in an investigational study within 30 days of enrollment; participated in biologic investigational studies within 90 days of enrollment, or subjects planning to participate in any other interventional clinical research study while enrolled in this trial.
9. Subjects with known immunosuppression or immunosuppressive illness.
10. Subjects with uncontrolled diabetes or autoimmune disorders.
11. Use of concomitant medications that have the potential to prolong bleeding times such as anticoagulants or inhibitors of platelet aggregation (e.g., aspirin or other nonsteroidal anti-inflammatory drugs, Omega 3 or Vitamin E), within 14 days prior to surgical procedures. Omega 3 and Vitamin E were acceptable only as part of a standard multivitamin formulation.

6.5 Concomitant Therapies

All treatments and therapies used 30 days prior to enrollment (visit 1/screening) or 90 days prior to enrollment for biologics and all treatments or therapies used during the course of the study must be recorded in the Case Report Form (CRF) or electronic Case Report Form (eCRF).

6.5.1. Authorized Therapies

Unless listed under the exclusion criteria (Section 6.4) or in Prohibited Therapies (Section 6.5.2), other therapies to treat ongoing conditions are authorized.

6.5.2. Prohibited Therapies

None other than as specified in the Inclusion/Exclusion criteria.

Protocol Version 1:

This document contains confidential, proprietary information.

Protocol GLI.04.US.SL.017

CONFIDENTIAL

The decision to administer a prohibited medication/treatment should be made with the safety of the subject being the primary consideration. Whenever possible, Galderma Laboratories, L.P. should be notified before the prohibited medication/treatment is administered to discuss possible alternatives.

If a subject receives prohibited therapy during the study, the subject may be allowed (at the discretion of the investigator / Galderma Laboratories, L.P.) to continue in the study for safety evaluation purposes, only.

7. STUDY TREATMENT

The term “study treatment” refers to the study product (see Section 7.1)

7.1 Product Identification and Use

Study product: Cetaphil® Healing Ointment	
Form	Opaque ointment
Mode of Administration	Topical
Formula code	1748
Formula number	B50H48
Lot numbers	0281N14C
Storage and Handling	The product is to be stored under controlled room temperature conditions 20°C to 25°C (68°F to 77°F), protected from freezing and sunlight.

The ingredient list of the study product is included in Appendix I.

7.2 Additional Products and Materials

The Sponsor will only provide Cetaphil® Healing Ointment for the study. The study overhead will cover any additional materials or supplies.

7.3 Study Product Accountability

Upon receipt of the study products, the investigator or designee will conduct an inventory. In accordance with federal regulations, the investigator must agree to keep all test articles in a secure location with restricted access. Designated study personnel will provide the test article to the subjects in accordance with the protocol.

During the study, the investigator must maintain records of study treatment dispensation and collection for each subject. This record must be made available to the study monitor for the purposes of verifying the accounting of clinical supplies. Any discrepancies and/or deficiencies between the observed disposition and the written account must be recorded along with an explanation. At the conclusion of the study, the investigator will be responsible for returning all unused study product (i.e., Cetaphil® Healing Ointment) unless otherwise instructed by the Sponsor. Shipping label and cost will be provided to the investigator by the Sponsor.

Protocol Version 1:

This document contains confidential, proprietary information.

Protocol GLI.04.US.SL.017

CONFIDENTIAL

7.4 Method of Treatment Assignment

Subjects will be numbered sequentially in the order in which they qualify for entry into the study.

7.5 Treatment Product Dispensing

All treatment products will be administered only to subjects enrolled in the study, at no cost to subjects, and in accordance with the conditions specified in the protocol.

7.6 Treatments Compliance

Subjects will complete a daily diary, recording treatment product applications and comment during the study. Treatment product and diaries will be dispensed to subjects at Day 0 and reviewed for compliance at Day 28 visit. Treatment product will be visually inspected and weighed prior to distribution at Day 0 and at Day 28. Subjects will be instructed to return the treatment product and daily diary at Day 28 visit. If subjects do not return their treatment product or diary at the end of the study, a verbal confirmation will be obtained for usage compliance, and it will be documented as a note to file.

Any suspected noncompliance with the treatment product or study instructions will be addressed by the Investigator or clinic staff. The Investigator will determine whether a subject's noncompliance will affect the study outcome and whether the data should be excluded from statistical analyses.

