9.1.3. Visit 3 (Day 7 or Day 14 ± 2 days)

1. Clinic staff or Investigator will record any AEs that are observed or reported.
2. The surgical site will be assessed in the following:
 - a. Clinical grading by Investigator as described in section 10.1
 - b. Tolerability assessment by the subjects as described in section 10.2
 - c. Standardized photography as described in section 10.3
 - d. Self-assessment questionnaire as described in section 10.4
3. Clinic staff or Investigator will collect and review the treatment product and diary for compliance purpose.

Protocol Version 1:

This document contains confidential, proprietary information.

4. Subjects will be scheduled for a follow-up visit at Day 28 (± 3 days) and dismissed from the Clinic.

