10.1 Clinical Grading by Investigator

Investigator will perform clinical grading at the surgical site on each subject at baseline (pre- and post-procedure), day 7/14, and day 28. Investigator will grade the severity of wound parameters based on a visual analog scale, described in the table below (for erythema, edema, overall wound appearance, half-point scores can be used as necessary to better describe the condition):

Parameters	Score 0	Score 1	Score 2	Score 3
Erythema	None/absent	Mild	Moderate	Severe

Protocol Version 1:

This document contains confidential, proprietary information.

Edema	None/absent	Mild	Moderate	Severe
Overall wound appearance	Excellent (absent of wound)	Good (slightly visible wound)	Fair (moderately visible wound)	Poor (marked visible wound)

Parameters	Score 0	Score 1	Score 2	Score 3	Score 4
Scabbing/crusting	None	Slight (up to 30%)	Moderate (31-60%)	Extensive (61-90%)	Almost complete or complete (91-100%)

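### Section 7.6 lets the investigator who grades the wound decide case by case whether a noncompliant subject's data are excluded, and Section 11 sets no analysis population and no analysis with and without exclusions

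*Combined protocol and SAP*

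**What the plan says.** Section 7.6 has a wide trigger: "Any suspected noncompliance with the treatment product or study instructions will be addressed by the Investigator or clinic staff". It then gives one role the decision on the data: "The Investigator will determine whether a subject's noncompliance will affect the study outcome and whether the data should be excluded from statistical analyses". It states no compliance threshold, no deadline, no second reader and no requirement to be unaware of the scores.

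The same role produces the clinical outcome. Under Section 10.1, "Investigator will perform clinical grading at the surgical site on each subject" at every time point. There is one product, and no masked assessor is described.

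On timing, Section 7.6 says: "Treatment product and diaries will be dispensed to subjects at Day 0 and reviewed for compliance at Day 28 visit". Sections 9.1.3 and 9.1.4 list grading and tolerability scoring as step 2 and the compliance review as step 3: "Clinic staff or Investigator will collect and review the treatment product and diary for compliance purpose".

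Section 11 names no analysis population, missing-data rule or sensitivity analysis. Percent improved or worsened is divided by "total number of subjects", without saying whether an excluded subject still counts. The test for clinical grading and for tolerability is "Paired t-test; If normality fails, a Wilcoxon signed-rank test will be used", two-sided at 0.05. For tolerability the stated reading is "A decrease in scores or lack of significant increase indicates tolerability/safety of the treatment product".

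**The concern.** The only criterion for exclusion is whether noncompliance would affect the outcome. That is a judgement about the result, made by the person who grades it and possibly made after grading. An exclusion rule that can depend on outcome can bias everything Section 11 reports: the mean change, the percent improved or worsened, and the tests.

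Tolerability is exposed in a particular way. A subject whose wound burns may apply less ointment, which makes that subject noncompliant. Excluding the subject removes an unfavourable score and also lowers N. Because Section 11 counts the absence of a significant increase as evidence for the product, both effects push towards the favourable reading.

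Two kinds of noncompliance are foreseeable: fewer than two applications a day (Section 8.3.2), and use of another topical on the site, which Section 8.3.4 bars.

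**Working it through.** The plan gives no figure to reproduce: there is no power calculation, effect size, SD or dropout rate. The inputs are 20 completers (Section 6.1), two-sided alpha 0.05 and the tests and formulas in Section 11. The number of exclusions and the pattern of scores below are assumptions.

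**Percent improved or worsened, x of 20, one subject excluded, denominator 19.**
- The excluded subject had improved: (x − 1)/19 − x/20 = (x − 20)/380. This is −5.0 points at x = 1 and 0 at x = 20.
- The excluded subject had not improved: x/19 − x/20 = x/380. This is 0 at x = 0 and +5.0 points at x = 19.
- At x = 10 the shift is 10/380 = 2.6 points, down or up.
- If the denominator stayed at 20, losing an improver would cost 1/20 = 5.0 points and losing a non-improver would change nothing. The 5.0-point bound holds on either reading.

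**Two excluded, denominator 18, both improved or both not.** The shift is (x − 20)/180 or x/180, at most 10.0 points (x = 2 or x = 18).

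**Mean change.** If the mean is m and the excluded change is y, the new mean is (20m − y)/19 = m + (m − y)/19. A subject d points from the mean shifts it by d/19: 0.053 for d = 1 and 0.158 for d = 3.

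**Tolerability reading at the margin.** Assume k subjects increase by 1 and all others do not change, with zeros dropped from the Wilcoxon test. The exact p is 2 × 0.5^k. In the normal approximation with tie correction and no continuity correction, z = √k. Section 11 does not say which version applies.

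| Increases | Exact Wilcoxon p | Approximate Wilcoxon p |
|---|---|---|
| 6 in 20 | 0.031 | 0.014 |
| 5 in 19 | 0.063 | 0.025 |
| 4 in 20 | 0.125 | 0.046 |
| 3 in 19 | 0.25 | 0.083 |

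The exact version crosses 0.05 when 6 in 20 becomes 5 in 19. At 5 in 19 the approximate version is still significant, and so is the paired t-test (p about 0.021). The approximate version crosses when 4 in 20 becomes 3 in 19, as does the paired t-test (0.042 to 0.083). Under the exact version 4 in 20 was never significant. So each method has a point at which one exclusion changes the reading, but the points differ.

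**Does the exclusion rule matter, or only the loss of subjects?** A simulation of the paired t-test (200,000 runs, normal changes, no true change, N = 20) compared two extremes. When the subjects with the worst changes are always the ones removed, two-sided rejection rises from 0.051 to 0.089 with one excluded and 0.161 with two. When removal is unrelated to outcome, it stays at about 0.05 with one to four excluded. The harm comes from dependence on outcome, which a pre-specified rule removes.

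**The case against.** The case against has several fair parts.

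- *Knowledge of the scores is inferred.* The visit lists are numbered but not declared sequential, clinic staff may do the compliance review, and no text says when exclusion is decided. This stands: the documents support only that the scores may be known.
- *Tolerability is scored by subjects (Section 10.2).* The conflict between grading and excluding therefore applies directly only to clinical grading. For tolerability, the weaker point remains that the investigator may see the scores.
- *Section 6.5.2 may already cover other topicals.* Inclusion criterion 9 and exclusion criterion 6 may bring Section 8.3.4 into the prohibited therapies by general wording. Such a subject could then be allowed to continue for safety assessment alone. This stands as a possibility: Section 7.6 may not be the only rule. But 6.5.2 is also discretionary and names no analysis set.
- *The study is small, has one product and is largely descriptive.* There is no randomisation to preserve. Even so, Section 11 plans tests at 0.05 and draws a safety conclusion from them.

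A reader might infer that safety information would be lost. The documents do not support that. Section 7.6 removes data only from the statistical analyses. Section 12 separately requires clinically relevant unfavourable changes in study parameters to be reported as adverse events whatever their cause.

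**Conclusion.** The concern holds as a defect in the rule. Following the plan as written permits exclusion that depends on outcome, and nothing in Section 11 would reveal it. One exclusion moves the percent improved or worsened by at most 5.0 points, and by 2.6 points at 10 of 20 with the denominator at 19. It moves the mean change by d/19. It can change the tolerability reading only near the significance margin, at a point that depends on the version of the test. The p-values rest on the assumed pattern of +1 and 0 changes.

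Two stronger readings are tempting. One is that results will be biased in favour of the product, with error rates such as 0.089 or 0.161. Those figures assume that the worst outcomes are always the ones removed, and nothing in the documents says so; the size and direction of any bias cannot be estimated. The other is that a single exclusion generally reverses the tolerability conclusion. It does not: away from the margin the reading is unchanged.

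**What to change.** Replace the last sentence of Section 7.6 and add a paragraph to Section 11 with these elements.

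1. All treated subjects with post-baseline data stay in the main clinical-grading and tolerability analyses, and in the denominator of the percentages, regardless of compliance.
2. A sensitivity summary of mean change and percent improved or worsened is reported under major-deviation criteria written before any data review. It leaves out (a) scores after first use of a non-study topical on the site, other than sunscreen or the cleansing in Section 8.3.1; and (b) scores at a visit where diary applications up to that visit fall below a stated share of those expected. The documents give no threshold for (b), so the sponsor must choose one.
3. For (b), expected applications are counted only after the 36–48 hour bandage period in Section 8.3.1. At two a day that period covers 3 to 4 applications, and 4 is 29% of the 14 due by Day 7. Without this allowance, subjects who obeyed the bandage instruction could be flagged.
4. Existing sponsor data-management or statistics staff apply the criteria from the diary, product weights and therapy records, and each exclusion is listed.

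In Section 6.5.2, cross-refer to Section 8.3.4 and state how its provision for continuing for safety assessment alone maps to the main and sensitivity analyses.

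The cost is one sentence replaced, one paragraph, one extra summary, one clarification and some staff time. No new visit or assessment is needed. Whether a CRF item must be added cannot be checked, because the CRF and diary forms are not in the documents. The downside is that the main estimate includes some poorly compliant scores; the sensitivity summary shows how much they matter.
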